4.2.1 Discontinuation From Study Vaccine

Only a single dose booster vaccination will be administered to each participant; thus, discontinuation from study vaccine is not applicable.

4.2.2 Withdrawal From the Study

If a participant withdraws or is withdrawn from the study, the ET procedures as indicated in the SOE (Table 13-1) should be completed.

The investigator will also withdraw a participant if the sponsor terminates the study.

4.2.3 Lost to Follow-Up

A participant will be considered lost to follow-up if he or she repeatedly fails to return for scheduled visits and is unable to be contacted by the study site.

The following actions must be taken if a participant fails to return to the clinic for a required study visit:

- The site must attempt to contact the participant and reschedule the missed visit as soon as possible and counsel the participant on the importance of maintaining the assigned visit schedule and ascertain whether the participant wishes to and/or should continue in the study.
- Before a participant is deemed lost to follow-up, the investigator or designee must
 make every effort to regain contact with the participant (where possible, 2 telephone
 calls and, if necessary, a certified letter to the participant's last known mailing address
 or local equivalent methods). These contact attempts should be documented in the
 participant's medical record.

If the participant continues to be unreachable, he/she will be considered to have withdrawn from the study.

4.2.4 Replacements

Participants who withdraw may be replaced at the discretion of the sponsor after consultation with the SRT. In particular, any participants who are assigned to a group in error and not

Protocol 217741 (CV2 SARS-COV2-002 BST) Amendment 2

13 Jun 2022

vaccinated may be replaced. In general, participants who withdraw for reasons connected to the study vaccine (eg, safety concerns after study vaccination) should not be replaced.

5 Study Vaccines

5.1 Method of Assigning Participants to Study Vaccine Groups

Participants will receive study vaccine on Day 1 according to a specific cohort, dose group, and age group. Interactive response technology will be used to track enrollment. Biostatistics will generate the treatment schedule using SAS software Version 9.4 or later (SAS Institute Inc, Cary, North Carolina) for IRT, which will link sequential participant numbers to treatment codes. Note: If a participant is consented electronically, a participant number may be generated; however, that number will be updated to align with the IRT number after enrollment is complete for consistency in each participant's study records.

[figure not shown]
5.2 Study Vaccines Administered

Study vaccine will be administered on Day 1. Study vaccine will be administered as a single IM injection of 0.3 mL in the deltoid area, preferably in the nondominant arm.

Refer to the IB and Pharmacy Manual for further details regarding the study vaccine preparation and administration.

5.3 Identity of Investigational Product

Investigational product refers to the CV2CoV vaccine that will be administered during the study.

GSK Biologicals SA and/or CureVac will provide adequate supplies of IP to PPD for distribution to the study sites. The following IP will be used in the study:

Table 5-1 Investigational Product Information

	Investigational Product
Description	CV2CoV ^a
CCI	CCI
CCI	WT CCI
CCI	CCI

Product reference: CV07050201.

b. CCI

The LNP encapsulated mRNA product, CV2CoV, is supplied in glass vials as a sterile colloidal dispersion in a frozen liquid formulation. A diluent will be used to dilute the products to the appropriate dose levels.

Refer to the Pharmacy Manual for any details regarding blinding requirements, storage, and preparation for the IP.

5.4 Management of Clinical Supplies

5.4.1 Investigational Product Packaging and Storage

Investigational product will be supplied in vials that will require further dilution and preparation procedures; please refer to the Pharmacy Manual for additional packaging and preparation details. The IP must be stored in a secure, restricted freezer and kept at the temperature noted in the Pharmacy Manual at each stage of preparation for IM administration.

Once prepared and diluted for IM administration, refer to the Pharmacy Manual for storage conditions. The investigator or designee must confirm appropriate temperature conditions have been maintained during transit for all IP received and any discrepancies are reported and resolved before use of the IP.

Refer to the Pharmacy Manual for further details regarding storage and preparation requirements.

5.4.2 Investigational Product Accountability

The investigator will maintain accurate records of receipt of all IP, including dates of receipt. In addition, accurate records will be kept regarding when and how much IP is administered to each participant in the study. Only participants enrolled in the study may receive the IP and only authorized site personnel may supply or administer the IP. Reasons for departure from the expected dispensing regimen must also be recorded. At the completion of the study, to satisfy regulatory requirements regarding drug accountability, all IP will be reconciled and retained or destroyed according to applicable regulations. Further guidance and information for the final disposition of unused IP are provided in the Pharmacy Manual.

5.4.3 Other Supplies

Refer to the Pharmacy Manual for ancillary formulation preparation or injection materials that will be distributed by PPD to the study sites or that the study sites will need to procure.

5.5 Overdose Management

An overdose is any dose of study vaccine given to a participant that exceeds the planned dose for an individual within a given dose group.

There is no specific treatment recommended for an overdose.

Any overdose must be promptly reported to PPD within 24 hours. Overdose itself is not to be reported as an AE. However, any AEs associated with the overdose are to be reported in the relevant AE/SAE sections of the eCRF.

In the event of an overdose, the investigator should:

- 1. Contact the medical monitor immediately.
- 2. Closely monitor the participant for any AE/SAE and laboratory abnormalities for at least 3 days.
- 3. Document the quantity of the excess dose in the eCRF.

Decisions regarding any overdoses will be made by the investigator in consultation with the medical monitor based on the clinical evaluation of the participant.

5.6 Blinding

Participants will receive study vaccine as described in Section 5.1. The study will be open-label. The laboratories responsible for immunogenicity analyses will be blinded.

In the event of a quality assurance audit, auditors will be allowed access to study vaccine records at the study sites to verify that dispensing was performed accurately.

A statistical and programming team may perform interim analyses during the study. Unblinded safety and immunogenicity summaries, if applicable, will be provided to the SRT to inform study decision for progressing enrollment (Section 7.8).

5.7 Compliance With Study Vaccine

All participants will be vaccinated at the study site by the investigator or designee, under medical supervision. The date and time of study vaccine administration will be recorded in the source documents and in the eCRF. The dose of study vaccination and participant

identification will be confirmed at the time of dosing by a member of the study site personnel other than the person administering the study vaccination.

When the individual dose for a participant is prepared from a bulk supply, the preparation of the dose will be confirmed by a second member of the study site personnel.

5.8 Prior, Concomitant, and Rescue Medications, Vaccines, and Therapies

5.8.1 Prior and Concomitant Medications

Use of all prior and concomitant medications (within 6 months of Screening) and vaccinations (within 18 months of Screening) will be recorded in the participant's eCRF. The minimum requirement is that drug name and the dates of administration are to be recorded. This will include all prescription drugs and vaccinations. In addition, any herbal products, vitamins, minerals, and over-the-counter medications taken within 2 weeks of study vaccination should also be recorded in the participant's eCRF. Any changes in concomitant medications also will be recorded in the participant's eCRF throughout the study.

5.8.2 Allowed Concomitant Therapy

Any concomitant medication deemed necessary for the welfare of the participant during the study may be given at the discretion of the investigator. However, it is the responsibility of the investigator to ensure that details regarding the medication are recorded in full in the eCRF.

The following concomitant therapies are allowed during the study:

- Acetaminophen/paracetamol
- Contraception, as described in Appendix 13.2
- Low-dose topical, ophthalmic, inhaled, and intranasal steroid preparations
- Local intra-articular steroids that are expected to remain localized in the joint space in which they are administered
- Inactivated influenza vaccines are allowed if received at least 14 days before or after study vaccination. Note: If other nonstudy vaccines are received during the study, participants may continue to complete the remaining study assessments. Any impact on the immunogenicity data will be addressed in the data analysis.

 Participants may take concomitant medications for management of medically stable chronic conditions as long as the medication and medical conditions are not exclusionary (Section 4.1.2)

Participants will be allowed to receive a booster dose of a licensed or authorized (conditional regulatory approvals, including emergency use authorizations are acceptable) COVID-19 vaccine, per national recommendations, if received after the Day 29 visit.

No concomitant medications will be provided by the sponsor or PPD.

5.8.3 Rescue Medicine

There are no known rescue medications for the IP; supportive care should be provided to participants.

5.9 Study Holding Rules

The study holding rules in Table 5-2 will be applied independently to each dose group.

Table 5-2 Study Holding Rules

Study Holding Rule	Study Holding Rule Description	Number of Participants Needed to Trigger a Study Hold
1a	Death or any life-threatening SAE regardless of causality	≥1
1b	Any non-life-threatening SAE that cannot be reasonably attributed to a cause other than vaccination as per investigator or Sponsor assessment	≥1
1c	Any withdrawal from the study (by investigator or participant request) following a Grade 3 AE	≥1
1d	Any local or general solicited AE leading to hospitalization OR necrosis at the injection site; each with an event onset within the 7-day postvaccination period (Days 1 to 7)	≥1
1e	Severe cases of SARS-CoV-2 infection	≥2
1f	Any same or similar Grade 3 related unsolicited events, including but not limited to the identical MedDRA high-level term	≥2
1g	Same Grade 3 solicited local or systemic AE in an investigational group	>3
1h	Same Grade 3 or above abnormality in prespecified hematological or biochemical laboratory parameters with an event onset by Day 8 (± 1 day) postvaccination, except nonclinically significant lymphopenia	≥3
2a	Any Grade 3 solicited events in an investigational group, with an event onset within the 7-day postvaccination period (Days 1 to 7)	2 out of 3 first exposed participants 3 out of 5 first exposed participants 7 out of 16 first exposed participants 9 out of 22 first exposed participants 11 out of 28 first exposed participants 12 out of 30 first exposed participants (combined younger and older adult age groups)
2b	Any Grade 3 unsolicited AE , that can be reasonably attributed to the vaccination as per Investigator or Sponsor assessment, with an event onset within the 7-day (Days 1 to 7) postvaccination period	2 out of 15 first exposed participants 3 out of 30 first exposed participants (combined younger and older adult age groups)

Study holding rules 1a through 1d will be assessed by the investigators on a continuous basis. Study holding rules will lead to a halting of the entire study, with the exception of study

holding rule 1c, which will lead to halting of the concerned cohort and the next cohorts with higher doses.

Study holding rules 1e, 1f, 1g, 1h, 2a and 2b will be assessed by the SRT on an ongoing basis. An adaptive Bayesian logistic regression model will be used during SRT meetings (scheduled or ad-hoc according to Table 5-2) to evaluate the posterior probability for the percentage of severe solicited AEs at the current and the next dose (Appendix 13.3). A lower than 50% posterior probability, that the percentage is above the maximal tolerable dose, will be favorable to progress at the next dose. Each study holding rule will be applied per cohort and age group. Based on the historical Phase 1 data from CVnCoV, Moderna and Pfizer mRNA COVID vaccines, the maximum tolerable rate has been set up to 30%.

The SRT will review all available safety data at scheduled time points and at the time when any of the study holding rules are met. A recommendation will be made to the sponsor on whether a cohort or group should be permanently stopped, modified, or continued unchanged. If a study holding rule is met, it will be escalated according to process to the SRT who will decide whether other participants can be enrolled/vaccinated. Medical judgment, taking into account all available safety data at the time of review, should be the basis for decision to continue the study or not.

In the event of a halting of the study, ethical and regulatory authorities will be notified per local requirements.

6 Study Assessments and Procedures

Before any study procedures are performed, all potential participants will be consented using an IRB/IEC-approved ICF. Additional procedural details related to the ICF are provided in Section 9.3. Study assessments will be performed in an outpatient setting at qualified study sites. Due to the ongoing pandemic, safety follow-up visits may be completed via televisits, as permitted by country regulations. In-person visits should be maintained in the study unless there is a public health emergency limiting access to study sites. During such an emergency or extenuating circumstance, televisits can be employed to keep personal access to subjects and ascertain their safety at a high level.

Refer to the SOE table in Appendix 13.1 for a full list of visits and assessments (Table 13-1).

A maximum of 150 mL of blood will be collected per participant per visit. This may include 50 mL of blood collected at 2 visits for participants enrolled at sites where PBMCs are collected (ie, cell-mediated immunity subset). The maximum amount of blood collected over the 6-month duration of the study is approximately 800 mL. Repeat or unscheduled samples may be taken for safety reasons or for technical issues with the samples.

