3.1 Study Design

This Phase 1 study will evaluate the safety, reactogenicity, and immunogenicity of the CV2CoV vaccine in SARS-CoV-2 seropositive healthy adult participants. The study will be conducted in 5 sequential cohorts with dose escalation from 2 μg to 20 μg. A total of up to approximately 180 healthy adult participants will be enrolled, 30 per dose group as indicated in Table 3-1. The 30 participants will be distributed between the younger (≥18 to <65 years old) and older (≥65 years old) age groups, with a minimum of 10 and a maximum of 20 participants in each age group. There will be 3 sentinel participants in each age group within each dose group. A study design schematic is provided in Figure 3-1.

Table 3-1 CV2CoV Study Cohorts, Dose Groups, and Dose Levels

Cohort	Dose Group	Dose Level	Younger Adults ≥18 to <65 Years of Age	Older Adults ≥65 Years of Age	Total Dose Group Sample Size
1	1a	2 μg	$10 \le n \le 20$	$10 \le n \le 20$	30
	1b	4 μg	$10 \le n \le 20$	$10 \le n \le 20$	30
2	2	8 μg	$10 \le n \le 20$	$10 \le n \le 20$	30
3	3	12 μg	$10 \le n \le 20$	$10 \le n \le 20$	30
4	4	16 µg	$10 \le n \le 20$	$10 \le n \le 20$	30
5	5	20 μg	$10 \le n \le 20$	$10 \le n \le 20$	30

Note: The first 3 participants enrolled in each age group within each dose group will be sentinel participants.

The screening period will be up to 14 days, study vaccine administration will occur on Day 1, and participants will have approximately 180 days (6 months) of follow-up after study vaccine administration. Study assessments will be performed in an outpatient setting at qualified study sites.

The study will be open-label. Participants in all cohorts will be screened for eligibility up to 14 days before enrollment. Participants will receive study vaccine according to their cohort (Table 3-1), dose group, and age group; and study visits will proceed according to the SOE (Table 13-1). Participants will be sequentially enrolled to the dose level assigned to their cohort.

Enrollment in each dose cohorts and the progression from vaccination in younger to older adult participants will be staggered based on SRT data review will progress as described in Section 7.8. Holding rules for dosing are described in Section 5.9.

[figure not shown]

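### Protocol Section 5.9 gives incompatible counting units for the holding rules that need more than one participant, so the same events can meet a hold or not

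*Protocol*

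**What the plan says.** All of this is current Amendment 2 text.

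- Protocol Section 5.9, opening sentence: "The study holding rules in Table 5-2 will be applied independently to each dose group".
- Table 5-2, rules 2a and 2b: the words "combined younger and older adult age groups" follow the last step (12 of 30 and 3 of 30). The table does not say whether they cover only that step or the whole cell.
- Table 5-2, rule 1g, threshold more than 3: "Same Grade 3 solicited local or systemic AE in an investigational group". Rule 2a uses the same group term. Neither document defines it.
- Section 5.9, after the table: "Each study holding rule will be applied per cohort and age group". The neighbouring sentences concern the Bayesian logistic regression model.
- Consequence, with an exception for rule 1c: "Study holding rules will lead to a halting of the entire study".
- Section 3.1: each dose group has 30 participants, "with a minimum of 10 and a maximum of 20 participants in each age group". Table 3-1 puts two dose groups, 2 µg and 4 µg, in Cohort 1. Its note says: "The first 3 participants enrolled in each age group within each dose group will be sentinel participants".

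The SAP (Section 3.1) only refers back to protocol Section 5.9 for the holding rules.

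**The concern.** Rules 1a to 1d fire at one participant, so the counting unit does not affect them. Rules 1e to 1h, 2a and 2b need two or more, and for these the number counted depends on whether the two age groups of a dose are added together and, in Cohort 1, whether the two doses are.

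This is a first-time-in-human dose escalation, and the SRT is asked to assess exactly these rules. If members work from different sentences of the same section, one can report that a study-wide hold has been met while another, with the same data, reports that it has not.

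**Working it through.** **1. Can both sentences be obeyed?** Table 5-2 gives the 2a steps as 2/3, 3/5, 7/16, 9/22, 11/28 and 12/30, and the 2b steps as 2/15 and 3/30. Section 3.1 caps an age group at 20 per dose group.

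| Place | Per dose group, ages together | Per cohort and age group, literally |
|---|---|---|
| Cohorts 2 to 5 | n = 30, all steps reachable | n = 10 to 20; 2a steps at 22, 28, 30 and 2b step at 30 unreachable |
| Cohort 1 | 2 µg and 4 µg counted apart | 2 µg and 4 µg merged, up to 20 + 20 = 40 per age group |

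The literal reading therefore switches off printed steps in four cohorts and pools doses in the fifth. With 15 or fewer in an age group the 2a step at 16 is also out of reach, and with fewer than 15 so is the 2b step at 15.

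**2. Concrete cases.**

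- *Rule 1g (more than 3).* Two younger and two older participants at one dose have the same Grade 3 solicited event. Pooled, 4 > 3 and the rule is met. By age, 2 and 2, and it is not.
- *Rule 2a, opposite direction.* None of 3 younger sentinels, then 2 of 3 older sentinels, have a Grade 3 solicited event. By age, the older group meets 2 of 3. Pooled in order of vaccination, it is 0 of the first 3 and at most 2 of the first 5, so no step is met by the sixth participant.

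**3. Probabilities.** The plan states no operating characteristics for the holding rules. Its only binomial figures, in Section 7.2, reproduce: 1 − 0.95^30 = 0.785 and 1 − 0.90^30 = 0.958.

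Assumptions: one dose group, 15 younger and 15 older, the same event rate in both ages, each rule taken alone. Event rates are mine, except that 30% is the protocol's maximum tolerable rate.

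Rules 1f, 1g and 1h, for **one named event type or laboratory parameter**, with k = 2, 4 and 3:

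- pooled = P(Bin(30, p) ≥ k)
- by age = 1 − [1 − P(Bin(15, p) ≥ k)]²

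Example, 1g at 10%: pooled 0.353; one age group 0.0556, so by age 1 − 0.9444² = 0.108.

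| Rule | Rate | Pooled | By age |
|---|---|---|---|
| 1f | 2% | 0.12 | 0.07 |
| 1f | 5% | 0.45 | 0.31 |
| 1g | 5% | 0.06 | 0.01 |
| 1g | 10% | 0.35 | 0.11 |
| 1h | 5% | 0.19 | 0.07 |
| 1h | 10% | 0.59 | 0.33 |

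Rule 2a, exact recursion with a look at each listed denominator the group reaches; by age = 1 − (1 − q₁)(1 − q₂), where q is the trigger probability in one age group:

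| Rate | Pooled, 30 | By age, 15/15 | By age, 20/10 |
|---|---|---|---|
| 20% | 0.14 | 0.22 | 0.24 |
| 30% | 0.41 | 0.45 | 0.50 |
| 40% | 0.76 | 0.66 | 0.77 |

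Counting by age gives two chances at the early steps but loses the later ones, which is why the direction changes. Rule 2b at 5% gives 0.25 pooled and 0.31 by age (15/15).

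**4. How often the sentinel case arises.** At 30%, P(at least 2 of 3 older sentinels) = 3 × 0.09 × 0.7 + 0.027 = 0.216. No pooled step is met by the sixth participant if either

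- no younger sentinel is affected: 0.343 × 0.216 = 0.074; or
- one younger sentinel is affected and only one of the first two older ones, plus the third: 0.441 × 0.126 = 0.056.

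The sum is 0.130, or 60% of 0.216.

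**The case against.** Four points can fairly be made.

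- *The opening sentence bars pooling across doses; it does not expressly pool ages.* This is right. For 1f to 1h one could count within dose and then within age and satisfy both sentences in Cohorts 2 to 5. A reader might infer a flat contradiction for every rule, and the text does not support that. The outright conflict lies in 2a and 2b, whose larger denominators need both ages, and in Cohort 1. For 1f to 1h the documents leave the unit unsettled.
- *The later sentence may have been meant for the Bayesian model.* Appendix 13.3 does apply the model guide by dose and age group, which makes this plausible. As written, though, it speaks of each holding rule. Reading cohort as dose level, as Section 7.2 does, removes the Cohort 1 problem but not the conflict over ages.
- *Rule 1e.* A reader might infer from Section 1.2 that its two severe COVID-19 cases are counted study-wide. That section says two cases hold the whole study, which gives the extent of the hold, in line with Section 5.9. It does not say over whom the two are counted.
- *Practical effect is limited.* The SRT reviews sentinel data before expansion and same-age-group data before escalation, so the older-sentinel case would reach it without a formal hold. Section 5.9 adds: "Medical judgment, taking into account all available safety data at the time of review, should be the basis for decision to continue". A separate SRT charter, not among these documents, may state the unit. This lowers the consequence. But judgment governs what follows a hold, not when one is met, and a charter should not have to overrule its protocol.

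**Conclusion.** The defect stands and should be fixed: a safety rule that can halt the study cannot be followed as written. It affects 1e to 1h, 2a and 2b only. The unreachable steps and the merging of doses follow from the printed numbers and need no assumption about event rates.

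The probabilities do rest on assumed common rates and a 15/15 split unless stated. The gap is wide for 1g (0.35 against 0.11 at 10%) and small for 2a at the 30% limit (0.41 against 0.45). The figures for 1f to 1h are for one named event type. The chance that a rule fires on any of several symptoms or parameters would be higher and was not computed.

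Two stronger conclusions are not supported: that either unit is uniformly the safer one, since 2a goes both ways, and that participants are left unprotected, since the SRT sees all available safety data.

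**What to change.** Delete or replace the later sentence in Section 5.9 so that it says the following.

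1. Rules are counted within each dose group, with 2 µg and 4 µg separate.
2. Rules 1f, 1g and 1h pool the two age groups. Within a dose group this is never less strict than counting by age.
3. The group term in 1g and 2a means the dose group.
4. Each 2a and 2b step states whether ages are combined. The steps at 22, 28 and 30 must be. The sponsor must choose for 3, 5 and 16 in 2a and for 15 in 2b, and should say so if 2 of 3 is meant for each age group's sentinel set.
5. The dose-and-age-group unit belongs to the Appendix 13.3 Bayesian guide.
6. Rule 1e states whether its two severe cases are counted study-wide.

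The cost is an amendment of wording in Section 5.9 and Table 5-2 and a check that the SRT charter agrees; no added participants or procedures.

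A further option is to hold under 2a or 2b if either the pooled or the by-age count is met. This is not needed to cure the defect and raises the hold rate. With sentinels first (3 younger, 3 older) and then alternating enrolment at 15/15, 2a goes from 0.14 pooled to 0.23 at a 20% rate, and from 0.41 to 0.52 at 30%. That choice is the sponsor's.
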